## **3.13. Follow-up Procedures**

### **3.13.1. 1-Week Follow-Up Visit; Required: Day 7 ( $\pm$ 3 days)**

A phone contact will take place one week after each treatment visit to evaluate the condition of the treatment area, pain score, and adverse events. If there are any observations reported at the phone follow-up, the subject will be contacted by phone weekly until resolution of symptoms is documented. If there is evidence that an adverse event may have occurred, the subject will be asked to come in for a visit so an appropriate evaluation can be done. Email may be used as an alternate method of contact.

### **3.13.2. 3-Week Follow-Up Visit; Required: Week3 ( $\pm$ 7 days)**

A phone contact will take place three weeks after each treatment visit to evaluate the condition of the treatment area, pain score, and adverse events. If there are any observations reported at the phone follow-up, the subject will be contacted by phone weekly until resolution of symptoms is documented. If there is evidence that an adverse event may have occurred, the subject may be asked to come in for a visit so an appropriate evaluation can be done. Email may be used as an alternate method of contact.

### **3.13.3. 6-Week Follow-Up Visit; Required: Week 6 ( $\pm$ 7 days)**

The following evaluations will be performed at the 6-week follow-up visit after Treatment Visit #1 and #2.

1. Obtain weight
2. Perform clinical assessment of the treatment area for any epidermal, dermal and subcutaneous findings (e.g., erythema, bruising, swelling, pigment changes).
3. Assess for alterations in sensation (e.g., numbness, tingling). Assess subject pain score using 0 – 10 scale.
4. Examine the oral cavity for evidence of dry mouth.
5. Assess lower face motor nerve function.
6. Assess for any adverse events.

### **3.13.4. 12-Week Final Follow-Up Evaluation; Required (12 weeks $\pm$ 14 days post final treatment)**

The following evaluations will be performed at the 12-week follow-up visit after the final treatment visit:

1. Obtain weight.
2. Obtain photographs using standardized setup and settings. In addition, 3-dimensional images may be captured.
3. Measure fat layer thickness of the treatment area with a commercially-available ultrasound device using a standardized protocol.
4. Perform clinical assessment of the treatment areas for any epidermal, dermal and subcutaneous findings (e.g., erythema, bruising, swelling, pigment changes).
5. Assess for alterations in sensation (e.g., numbness, tingling). Assess subject pain score using 0 – 10 scale.
6. Examine the oral cavity for evidence of dry mouth.
7. Assess lower face motor nerve function.
8. Assess for any adverse events.

9. Administer subject questionnaire to obtain subject feedback on overall satisfaction.

**3.13.5. Optional Follow-Up Evaluations (up to 4 within study period)**

The full evaluation is not required at optional follow-up visits; the extent of the assessment will be at the discretion of the investigator.

Table 2 summarizes study schedule and events at each visit.

**Table 2. Schedule of Assessments**

|                              | Screening
(< 1 hr) | Treatment
Visit #1
(< 4 hrs) | Post-Treatment Visit #1       |                               |  | Post-Treatment Visit #2        |                               |                        |                                | Optional **
Follow-Up |
|------------------------------|-----------------------|------------------------------------|-------------------------------|-------------------------------|--|--------------------------------|-------------------------------|------------------------|--------------------------------|--------------------------|
|                              |                       |                                    | 1 Wk
Follow-Up
(< 1 hr) | 3 Wk
Follow-Up
(< 1 hr) | 6 Wk Follow-Up
AND
Treatment Visit #2
(< 4 hrs) | 1 Wk Follow-
Up
(< 1 hr) | 3 Wk
Follow-Up
(< 1 hr) | 6 Wk
Follow-Up      | 12 Wk
Follow-Up
(< 1 hr) |                          |
| Time Frame                   | Day - 45 to 0         | Day 0                              | Day 7
(+/- 3 days)         | Day 21
(+/- 7 days)        | Week 6
(+/- 7 days)
6 Wk Tx #2                     | Day 7
(+/- 3 days)          | Day 21
(+/- 7 days)        | Week 6
(+/- 7 days) | Week 12
(+/- 14 days)       | Open                     |
| Informed Consent*            | X                     |                                    |                               |                               |  |                                |                               |                        |                                |                          |
| Inclusion/Exclusion Criteria | X                     | X                                  |                               |                               | X  |                                |                               |                        |                                |                          |
| Pregnancy Test               | X                     | X                                  |                               |                               | X  |                                |                               |                        |                                |                          |
| Medical History              | X                     |                                    |                               |                               |  |                                |                               |                        |                                |                          |
| Tx Site Assessment           | X                     | X                                  |                               |                               | X  |                                |                               | X                      | X                              |                          |
| Height                       | X                     |                                    |                               |                               |  |                                |                               |                        |                                |                          |
| Weight                       | X                     | X                                  |                               |                               | X  |                                |                               | X                      | X                              |                          |
| Photography                  |                       | X                                  |                               |                               | X***   |                                |                               | X***                   | X                              |                          |
| 3-D Photography              |                       | X***                               |                               |                               | X***   |                                |                               | X***                   | X***                           |                          |
| Thermal Imaging              |                       | X***                               |                               |                               | X***   |                                |                               |                        |                                |                          |
| Caliper Measurement          | X                     |                                    |                               |                               |  |                                |                               |                        |                                |                          |
| Ultrasound Measurement       |                       | X                                  |                               |                               | X***   |                                |                               | X***                   | X                              |                          |
| Treatment                    |                       | X                                  |                               |                               | X  |                                |                               |                        |                                |                          |
| Pain Assessment              |                       | X                                  | X                             | X                             | X  | X                              | X                             | X                      | X                              |                          |
| AE Assessment                |                       | X                                  | X                             | X                             | X  | X                              | X                             | X                      | X                              |                          |
| Subject Survey               |                       |                                    |                               |                               |  |                                |                               |                        | X                              |                          |

\* Informed consent to be signed by subject prior to the collection of any data or completion of any study procedures.

\*\* Investigator discretion as to timing and extent of follow-up assessment for optional visits.

\*\*\* Optional

ZELTIQ P/N: [REDACTED]

Protocol Number: ZA17-004

This document and the contents hereof are considered proprietary and confidential information of ZELTIQ Aesthetics, Inc. Disclosure to unauthorized individuals or dissemination, publication or copying is prohibited without prior written consent of ZELTIQ.

## 3.14. Assessments

Study-related assessments are described below.

### 3.14.1. Safety Assessments

The primary safety endpoint is the rate of device- or procedure-related adverse events 12 weeks post 2nd treatment. Safety will be monitored by documentation of adverse events and clinical assessment of the treatment site.

### 3.14.2. Photography

All pre-treatment and post-treatment photographs will be taken using the same method. A series of baseline and follow-up photographs of the treatment area will be taken using standardized set up, lighting, and camera settings to ensure consistency. Subsequent to basic processing, the photographs may be cropped or re-sized for comparison purposes but otherwise will not be re-touched or manipulated in any way except for normal processing for equalization of color and exposure. Any re-sizing of photographs is intended to account for differences in camera-to-subject distance only. Any cropping of photos is intended to ensure that pre- and post-treatment follow-up images are aligned both vertically and horizontally. Cropping and/or re-sizing of the photographs will be performed using the same methods for all study photographs.

Image files will be stored electronically by ZELTIQ and indexed by subject study identification code. Copies of subject photographic data will be filed at the clinical site.

In addition to standard photography, 3-Dimensional photographs and thermal imaging may also be captured. Three-Dimensional photography may be performed using a commercially available photography system, such as the Canfield VECTRA or similar device. Thermal images may be captured using a commercially available system, such as a FLIR or similar device.

### **3.14.3. Caliper Measurement**

Caliper measurements of the treatment areas will be taken at the screening visit.

### **3.14.4. Ultrasound Measurement**

Ultrasounds will be performed by a qualified representative of the sponsor.

### **3.14.5. Subject Satisfaction**

[figure not shown]
Subject satisfaction data will be collected via a written questionnaire at the 12-week post-final treatment. This questionnaire will be composed of 5-point Likert scale questions, as well as free-text responses. Subjects will be asked to determine overall satisfaction with the treatment. The choices will be: 1) very dissatisfied; 2) dissatisfied; 3) not sure 4) satisfied; 5) very satisfied.

## **3.15. Endpoints**

The objective of this study is to further evaluate the safety and efficacy of the ZELTIQ CoolSculpting System to contour along the jawline.

### **3.15.1. Primary Endpoints**

The primary endpoints of the study will be defined as follows:

### 3.15.2. Secondary Endpoints

Secondary endpoints in the study are as follows:

- [REDACTED]
- [REDACTED]

## 3.16. Statistical Analysis Plan

### 3.16.1. Statistical Methods: Overall Plan

Data will be summarized based on the nature of the data. Dichotomous (e.g., gender, independent photographic review) and ordinal (e.g., Fitzpatrick Skin type) data will be tabulated by category. The mean, standard error, maximum and minimum will be tabulated for continuous data (e.g., age,). The significance level will be two-sided 0.05 for all statistical tests.

### 3.16.2. Analysis Population

Analysis Populations are defined as following:

#### Per-protocol Population (PP):

The Per-protocol Population will consist of all treated subjects followed for 12 weeks post last treatment and with weight change of no more than five percent at the time the 12-week post final treatment images are taken. Since a weight change of more than 5 percent will affect the images, the primary efficacy analysis will be performed based on this study population. Subjects who do not complete treatment will not be included in the primary and secondary efficacy analyses.

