### **3.10. Study Enrollment**

Study Candidates who sign the informed consent, meet eligibility criteria and undergo initiation of study treatment are considered enrolled. Study treatment initiation is defined as the initiation of the cooling cycle after the placement of the applicator on the intended treatment area on the scheduled treatment day.

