### **3.11. Study Photography**

Study candidates who sign the informed consent and meet eligibility criteria will be required to have baseline photographs of the intended treatment area taken. Baseline photographs will be taken using a standardized system prior to receiving the first treatment, and may also have additional photographs taken at subsequent treatment visits. All subjects will return 12 weeks after final treatment to have photographs of the treated area taken before exiting the study, using the same system and setup as baseline photographs.

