### 3.12. *Study Treatment Procedures*

#### 3.12.1. **Treatment Visit #1; Required: Day 0**

1. All female subjects of childbearing potential will be asked to take a pregnancy test (urine) at the treatment visit. Exclude subject from participation if the results are positive.
2. Review and verify the subject continues to meet all eligibility criteria.
3. Obtain weight.
4. Obtain baseline standardized photographs using standardized setup and settings. In addition, 3-dimensional image may be captured.  
[REDACTED]

1. Clean the applicator per instructions in the Addendum to the User Manual.
8. Per Investigator's discretion, perform up to four additional cooling cycles to cover the intended treatment area [REDACTED] cycles per treatment visit). For additional cooling cycles, repeat Step 7 in Section 3.12.1
9. The need for post-treatment care is not expected for this study. Subjects will be encouraged to call the study site if they experience any unexpected effects (e.g., severe discomfort, severe and/or prolonged erythema, bruising, swelling; blistering, etc.) which may be related to the study.

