#### As-Treated Population (AT):

This population consists of all treated subjects regardless of whether they become pregnant or undergo weight change during the study.

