**Safety Population (SA):**

This population will consist of all treated subjects with safety evaluation after the treatment. This population should be identical to the AT population. The safety data analyses will be performed based on the Safety Population.

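### Subjects who do not complete treatment are removed from every primary and secondary efficacy analysis, not only from the per-protocol one, so the single-cohort percentages may be too high

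*Combined protocol and SAP*

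**What the plan says.** Section 3.16.2 opens the PP definition with "The Per-protocol Population will consist of all treated subjects followed for 12 weeks post last treatment" and adds that weight may have changed by no more than 5% when the 12-week images are taken. It justifies using this set for the primary efficacy analysis by the effect of weight change on the images. Its last sentence is "Subjects who do not complete treatment will not be included in the primary and secondary efficacy analyses".

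The same section defines an As-Treated population: "This population consists of all treated subjects regardless of whether they become pregnant or undergo weight change during the study". Safety is assigned to a separate set: "The safety data analyses will be performed based on the Safety Population". No readable analysis is assigned to As-Treated.

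On who counts as treated, section 3.10 says "Study treatment initiation is defined as the initiation of the cooling cycle after the placement of the applicator". On what is collected, section 3.11 says "All subjects will return 12 weeks after final treatment to have photographs of the treated area taken before exiting the study". Section 3.13.4 schedules ultrasound and the questionnaire at that visit, and section 3.14.5 says "Subject satisfaction data will be collected via a written questionnaire at the 12-week post-final treatment".

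The design is a single non-randomized cohort (section 3.1) of at most 45 treated subjects (section 3.6). Section 3.16.1 gives the independent photographic review as an example of dichotomous data. Section 3.16.3 summarises satisfaction as a percentage. The adverse-effects table in section 7.2 lists intolerable discomfort that interrupts or ends the procedure.

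**The concern.** A per-protocol set usually leaves out subjects who did not complete treatment, and that alone is no fault. Here the exclusion is written for the primary and secondary efficacy analyses as a whole. Read literally, it leaves no room for an efficacy analysis of all treated subjects.

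The stated reason concerns weight and does not explain why a non-completer with stable weight should be left out. Such a subject is due back at week 12, so the rule sets aside outcomes that the study plans to collect.

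Non-completion happens after treatment starts and may be related to outcome. A subject whose procedure was ended for discomfort has had less treatment and a worse experience, and may plausibly show less change and be less satisfied. No control arm shares the exclusion, so nothing offsets it. The photographic-review percentage is at stake, and so is the satisfaction percentage if it counts as secondary efficacy. For ultrasound the same exclusion would shift a mean.

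**Working it through.** **No figure of the plan to reproduce.** The readable text bases the sample size of 45 on judgement and gives no success rate, power or dropout rate. What follows is an illustration.

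**Inputs**
- N = 45 treated subjects (section 3.6, the maximum).
- k = number of non-completers excluded. Assumed 1, 3 or 5.
- p = success rate in PP. Assumed about 80%, with 60% and 90% as checks.
- q = success rate among the excluded. Unknown, so taken from 0 to 1.
- All other treated subjects are assumed to be in PP, with one yes/no outcome each.

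**Formula.** The all-treated rate is A = [(45 − k)p + kq]/45. Hence

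p − A = (k/45) × (p − q).

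PP is too high when q is below p, too low when q is above p, and unaffected when they are equal.

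**Results at p of about 80%**

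| k | PP | All treated, q = 0 | All treated, q = 1 | PP minus all treated (points) |
|---|---|---|---|---|
| 1 | 35/44 = 79.5% | 35/45 = 77.8% | 36/45 = 80.0% | +1.8 to −0.5 |
| 3 | 34/42 = 81.0% | 34/45 = 75.6% | 37/45 = 82.2% | +5.4 to −1.3 |
| 5 | 32/40 = 80.0% | 32/45 = 71.1% | 37/45 = 82.2% | +8.9 to −2.2 |

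Check of the formula at k = 5 and q = 0: (5/45) × 80.0 = 8.9 points. If 4 of the 5 succeed, q = 80% and the difference is zero.

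**Other PP rates at k = 5**
- 24/40 = 60.0%: all treated 24/45 = 53.3% to 29/45 = 64.4%, a difference of +6.7 to −4.4 points.
- 36/40 = 90.0%: all treated 36/45 = 80.0% to 41/45 = 91.1%, a difference of +10.0 to −1.1 points.

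**Scale against sampling error.** The exact 95% interval for 35/44 runs from 64.7% to 90.2%, about 25 points wide, so the effect of one non-completer is minor beside it. For 32/40 the interval is 64.4% to 90.9%, against 55.7% to 83.6% for 32/45. With five failures excluded, the whole interval moves.

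**The case against.** The case on the other side is substantial.

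- **Leaving out non-completers is ordinary per-protocol practice.** This stands for the PP analysis. It does not justify carrying the exclusion into all secondary efficacy.
- **Stops for intolerability are not hidden.** Section 7.2 lists them as adverse effects, and section 3.16.3 tabulates all adverse events. This also stands, but it does not put those subjects into the efficacy percentage.
- **The pool may be very small.** Additional cycles are discretionary ("Per Investigator's discretion, perform up to four additional cooling cycles to cover the intended treatment area") and the second visit is optional (section 3.12.2), so few subjects may count as non-completers. An interrupted procedure may also still be finished. This stands and limits the size.
- **Satisfaction may not be covered.** The exclusion concerns efficacy analyses, whereas section 3.16.3 calls satisfaction a secondary endpoint and names no population for it. That is why the point on satisfaction is conditional.

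Four stronger readings are tempting, and the documents do not support them.

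1. *The PP paragraph contradicts itself*, because its first sentence admits treated, followed, weight-stable subjects and its last removes some of them. The more natural reading is that a specific sentence narrows a general definition. That is loose drafting.
2. *The plan never defines completion.* Section 3.10 defines only initiation, but the treatment steps in section 3.12.1 are partly redacted and could hold a definition.
3. *The plan has no all-treated efficacy analysis.* The photographic and ultrasound analysis text in section 3.16.3 cannot be read and may contain one.
4. *The percentages are biased upward.* The direction depends on how non-completers fare, which the documents do not show. The sign reverses if they do better than PP.

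**Conclusion.** The point holds in a limited form. As written, section 3.16.2 takes non-completers out of all primary and secondary efficacy on a ground that does not cover them, although their week-12 outcomes are due to be collected. In a single cohort this may overstate the photographic-review percentage, and the satisfaction percentage if it is secondary efficacy.

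The size is (k/45) times the gap between the PP rate and the rate in the excluded. Under the assumptions above, it is at most about 2 points too high for one non-completer and about 9 for five, with a smaller possible error the other way. Neither the count nor either rate comes from the documents.

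This is a minor to moderate weakness. It is worth correcting because the remedy is cheap, and it does not invalidate the planned primary analysis.

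**What to change.** Keep PP as the primary analysis and make these changes before data review:

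1. Reword section 3.16.2 so that completing treatment is an explicit condition of PP and the exclusion applies to the PP analysis only.
2. Report photographic review and satisfaction in the As-Treated population beside PP. Use observed week-12 outcomes, and bracket missing ones by counting them first all as non-success and then all as success.
3. Report ultrasound change for all treated subjects with both scans.
4. Apply the weight exclusion in section 3.9 to PP only. Its two sentences state different scopes, first the primary effectiveness analyses and then efficacy analyses generally, and should be aligned with section 3.16.2.
5. Tabulate exclusions from PP by reason.

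If the unreadable text of section 3.16.3 already contains an As-Treated efficacy analysis, reconcile section 3.16.2 with it instead of adding another.

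Two minor clarifications can be made at the same time. State what counts as completion for analysis, including the status of one-visit subjects, if the redacted text does not. Reconcile section 2.1, which ties the final efficacy assessment to the second treatment, with section 3.13.4, which ties it to the final one.

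The cost is SAP wording and one more set of tables, with no new visits or measurements. The As-Treated percentages may be less favourable, and the bracket will be wide if many outcomes are missing. Some gaps are foreseeable, since section 3.9 does not require follow-up photographs or ultrasound of subjects who become pregnant.
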